10.5.7. Safety Monitoring Guidance

10.5.7.1. Drug Induced Liver Injury

Based on United States Food and Drug Administration guidance (FDA 2009) for drug induced liver injury, discontinuation of study treatment should be considered if any of the following occur:

- ALT or AST $> 8 \times$ ULN
- ALT or AST $> 5 \times$ ULN for > 2 weeks
- ALT or AST $> 3 \times$ ULN **and** Total Bilirubin $> 2 \times$ ULN, or international normalized ratio > 1.5
- ALT or AST $> 3 \times$ ULN with the appearance of fatigue, nausea, vomiting, right upper quadrant pain or tenderness, fever, rash, and/or eosinophilia ($> 5\%$)

Information on the grading and management of laboratory abnormalities according to assessment severity is provided in Appendix 2 and Appendix 3, respectively.

[REDACTED]

[REDACTED]

[REDACTED]

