APPENDIX 3: GUIDANCE FOR THE MANAGEMENT OF CLINICAL AND LABORATORY ADVERSE EVENTS

Clinical AEs and abnormal results of laboratory tests and safety assessments considered to be an AE by the Investigator should be graded according to the severity scale of the CTCAE.

[figure not shown]
Uniform guidance for the management of AEs is provided in [Figure 2](#).

[figure not shown]
Grade 3 and 4 clinically significant laboratory abnormalities should be confirmed by repeat testing within 3 calendar days of receipt of results and before study treatment discontinuation, unless such a delay is not consistent with good medical practice.

A clinically significant Grade 4 laboratory abnormality that is not confirmed by repeat testing should be managed according to the algorithm for the new AE grade.

Study treatment may be continued without dose interruption for a clinically non-significant Grade 4 laboratory abnormality (eg, Grade 4 creatinine kinase after strenuous exercise, or triglyceride elevation that is non-fasting or that can be medically managed) or a clinical event considered unrelated to investigational product.

Any questions regarding adverse event management should be directed to the medical monitor.

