[REDACTED]

[REDACTED]

[REDACTED]

[REDACTED]

[REDACTED]

E. Open Label Extension Efficacy Endpoints

These efficacy outcomes will be measured at scheduled visits up to 52 weeks: EASI, vIGA, SCORAD, BSA, pruritus NRS, POEM, DLQI, and Patient Global Assessment (PGA).

Dichotomous response outcomes derived from specific scores will also be assessed.

F. Safety Endpoints

- Incidence and severity of adverse events (AEs).
- Incidence and severity of laboratory abnormalities and change from Baseline in laboratory values (to include hematology, serum chemistry, coagulation, and urinalysis).
- Incidence of clinically significant vital sign abnormalities and changes from Baseline. [REDACTED].
- [REDACTED]
- Physical examination findings.
- Other safety endpoints ([REDACTED] ophthalmoscopy [REDACTED]).

4. Study Design

A. Design Overview

This is a Phase 2, multicenter, randomized, double-blind, placebo-controlled study that includes multiple periods: up to a 4-week Screening Period (to determine subject eligibility); a 12-week DB Treatment Period with a 4-week Safety Follow-Up (SFU) Period following the last dose of double-blind study treatment; and eligible subjects may enter a 52-week OLE Period also followed by a 4-week Safety Follow-Up Period.

Randomization will be stratified by vIGA score at Baseline (3 versus 4) and region [REDACTED]. Subjects will receive etrasimod 1 or 2 mg or placebo orally once daily in a double-blinded manner for 12 weeks. During the OLE Period, all eligible subjects will receive etrasimod 2 mg orally, once daily. The application of topical moisturizers will be required at least once daily for at least 1 week prior to randomization and throughout the study without change (i.e., type, frequency, application). [REDACTED]

[REDACTED]. Rescue therapy will be permitted for uncontrolled [REDACTED]

symptoms at the discretion of the investigator based on an exacerbation of disease severity or subject self-reporting of worsened symptoms.

B. Study Population

Subjects with chronic AD defined by Hanifin and Rajka criteria () that has been present for at least 1 year despite optimized skin care (i.e., use of emollients, avoidance of irritants) whose disease is not adequately controlled with topical therapies, or for whom those therapies are not advisable.

C. Sample Size Determination

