Efficacy and safety endpoints will be analyzed according to their windowed visits defined by actual overall study day (i.e. calculated relative to first dose date in the DB Treatment Period). If more than one visit occurs within a single visit window, then the analysis will take the one closest to the target day. If the 2 visits are equidistant from the target day, the later visit will be used. Some efficacy or safety data are not scheduled to be assessed at each post-baseline visit. If the assessment date is not in the analysis visit window, the analysis will take the post-baseline scheduled visit closest to the assessment date. If there are 2 scheduled visits equidistant from the assessment date, the later visit will be used. The below table provides details of each analysis visit window.

D. Covariate Adjustment in Primary Analysis

The primary efficacy analyses will adjust for baseline EASI score, baseline vIGA score (3 versus 4) and region [REDACTED]. Key secondary analyses will adjust for baseline vIGA score (3 versus 4) and region [REDACTED] as described in Section 8 Efficacy Analyses below.

E. Interim Analyses

No formal interim analysis of efficacy is planned. Periodic blinded assessments may be conducted to assess the assumption regarding the SD of the percentage change in EASI from Baseline to Week 12. The planned sample size will not be reduced as a result of the SD assessments.

F. Multiple Comparisons and Multiplicity

For DB Treatment Period: no formal testing strategy or adjustments of the Type I error will be employed for the primary and key secondary endpoints. Estimates and confidence intervals (CIs) for treatment groups and from pairwise comparisons will be reported in an exploratory manner.

[figure not shown]
For the OLE Period: no formal statistical testing will be performed. Only descriptive statistics will be provided.

G. Analysis Sets

The following analysis sets will be defined for the DB Treatment Period and OLE Period separately:

Table 2 Analysis Sets

Analysis Set	Description
DB Treatment Period	
Full Analysis Set (FAS)	The FAS includes all randomized subjects, irrespective of whether they received any study treatment.

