- TEAEs by SOC, PT, and maximum Common Terminology Criteria for Adverse Events (CTCAE) severity
- TEAEs by SOC, PT, and maximum relationship to the study treatment
- Non-serious TEAE by SOC and PT

Targeted Medical Events by PT and Category will be summarized for DB Treatment Period, OLE Period, and overall.

All AEs will be presented in a by-treatment, and by-subject listing, for the DB treatment and OLE Periods separately, detailing the verbatim term given by the investigator, the PT, SOC, onset date, end date, CTCAE grade, outcome, relationship to study treatment, action taken with study drug, other action taken, seriousness and criteria for seriousness. SAEs and AEs leading to study treatment discontinuation will also be presented in a separate listing.

D. Clinical Laboratory Results

Laboratory parameters from the central laboratory will be summarized by treatment group at each scheduled assessment time point. For continuous lab parameters (hematology, serum chemistry, coagulation, and urinalysis), absolute values and change from Baseline will be summarized using descriptive statistics. For the OLE Period, change from Baseline will be calculated for the DB baseline and OLE baseline separately. Associated laboratory parameters (e.g., hepatic

[REDACTED]

enzymes, renal function, and hematology) will be grouped and presented together.

Changes from Baseline in the out of reference range abnormality flags will also be summarized using shift tables at each post-Baseline visit.

Data listings by-treatment and by-subject will be provided for all laboratory parameters reported in the standard units provided by the central laboratory. Lab values outside of the standard reference range will be noted.

Local laboratory assessments will be displayed in a separate listing. Pregnancy test results will be listed.

E. Vital Signs

Descriptive statistics for absolute values and change from Baseline in vital signs (BP, HR, respirations, body temperature) will be presented by treatment group. For OLE Period, change from Baseline will be calculated for the DB baseline and OLE baseline separately.

At baseline and week 16, descriptive statistics for pre-dose measurements and change of vital signs values will be presented by treatment group [REDACTED] after treatment initiation. [REDACTED]

[REDACTED]

[REDACTED]

[REDACTED]

[REDACTED]

[REDACTED]

[REDACTED]

[REDACTED]

[REDACTED]

[REDACTED]

G. Physical Examination

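### Incidence and severity of laboratory abnormalities are a stated safety endpoint, but the SAP tabulates laboratory values only by visit, with no any-time incidence, no CTCAE grade and a window rule blind to severity

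*SAP*

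**What the plan says.** SAP 3.F lists as a safety endpoint "Incidence and severity of laboratory abnormalities and change from Baseline in laboratory values", covering hematology, chemistry, coagulation and urinalysis. Protocol 11.8.1 lists the same endpoint.

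SAP 9.D plans these outputs from central laboratory data:

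- By-visit summaries of continuous parameters: "absolute values and change from Baseline will be summarized using descriptive statistics". SAP 5.A includes the minimum and maximum among these statistics.
- By-visit shifts: "Changes from Baseline in the out of reference range abnormality flags will also be summarized using shift tables at each post-Baseline visit".
- Listings: "Data listings by-treatment and by-subject will be provided for all laboratory parameters reported in the standard units provided by the central laboratory", with out-of-range values noted. Local results get a separate listing.

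SAP 5.C applies visit windows to safety as well as efficacy endpoints: "If more than one visit occurs within a single visit window, then the analysis will take the one closest to the target day". Ties go to the later visit. There is no exception for the worse value.

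On conduct, protocol Appendix 3 states: "Grade 3 and 4 clinically significant laboratory abnormalities should be confirmed by repeat testing within 3 calendar days of receipt of results". Protocol 10.5.4 asks for clinically significant values to be repeated until they resolve, and for clinically relevant changes to be entered as adverse events. Protocol Appendix 2 calls for CTCAE grading of clinically significant laboratory abnormalities.

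**The concern.** The endpoint has three parts: how often abnormalities occur, how severe they are, and change from baseline. The by-visit descriptive statistics deliver the third. For the first two, the laboratory tables offer only a low/normal/high flag at each visit. By-visit counts cannot be added into a count of subjects, because the same subject may be flagged at several visits. A flag also carries no grade.

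The window rule adds a second problem. The worst results are the ones most likely to have extra draws close together, because the protocol asks for repeats. The rule then picks a value by its date.

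The size of an abnormality matters in this trial. Protocol 1.3 cites liver enzyme elevations with another drug of the class. Lymphocyte lowering is an expected effect (protocol 10.2.7). SAP Table 2 also records 9 subjects in the 2 mg group with dose interruption attributed to lymphocyte decrease, which is 9/40 = 22.5% of a planned arm. A below-range flag does not separate an expected fall from a severe one.

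**Working it through.** No power or sample size figure underlies this point. The check sets the endpoint against the tables and adds two illustrations.

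**1. Endpoint against outputs**

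| Part of the endpoint | From laboratory values (SAP 9.D) | From adverse event tables (SAP 9.C) |
|---|---|---|
| Change from baseline | By-visit descriptive statistics | – |
| Incidence per subject, any time | None | Only events recorded as AEs |
| Severity (CTCAE grade) | None; by-visit maximum only | Maximum CTCAE grade of recorded TEAEs |

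By protocol Table 11, with a normal baseline, ALT just above ULN is Grade 1 and ALT above 20 × ULN is Grade 4. Both are simply high in a reference-range shift. The by-visit maximum can expose one extreme retained value, but it does not count subjects at any grade.

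**2. By-visit rate against any-time incidence**

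SAP 4.E gives seven post-baseline double-blind visits (Weeks 1, 2, 4, 6, 8, 12 and 16). Assume the parameter is drawn at all seven, with a per-visit abnormality rate p. If the same subjects are abnormal throughout, any-time incidence is p. If visits are independent, it is 1 − (1 − p)^7. If different subjects are abnormal each time, it is 7p.

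| p (assumed) | Same subjects | Independent | All different |
|---|---|---|---|
| 2% | 2.0% | 1 − 0.98^7 = 13.2% | 14% |
| 5% | 5.0% | 1 − 0.95^7 = 30.2% | 35% |
| 10% | 10.0% | 1 − 0.90^7 = 52.2% | 70% |

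Identical by-visit tables fit every column.

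**3. Window rule**

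Let the scheduled draw fall s days from target, s = −3 to +3 (the ±3 day visit window in SAP 4.E), and the repeat r days later. The rule keeps the repeat when |s + r| ≤ |s|. Weight all combinations equally and assume both draws share a window. The lag from draw to repeat is not given, so several ranges are shown.

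| Assumed lag r | Combinations | Repeat kept | Scheduled value kept |
|---|---|---|---|
| 1–3 days | 7 × 3 = 21 | 8 (38%) | 13 (62%) |
| 2–5 days | 7 × 4 = 28 | 8 (29%) | 20 (71%) |
| 1–5 days | 7 × 5 = 35 | 11 (31%) | 24 (69%) |
| 1–6 days | 7 × 6 = 42 | 12 (29%) | 30 (71%) |

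For lags of 1–5 days, s = −3 contributes 5, s = −2 contributes 4, s = −1 contributes 2 and the rest 0, giving 11. The scheduled value is displaced only when that visit was early.

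Example: take the Week 8 target as Day 57 (7 × 8 + 1), matching SAP 8.A, where Week 12 ends on Day 85. A draw on Day 55 shows ALT 9 × ULN and a repeat on Day 58 shows 2 × ULN. The distances are 2 and 1, so the by-visit tables keep 2 × ULN. Conversely, with a scheduled draw on Day 57, a higher value on Day 60 is left out.

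**The case against.** The strongest defence is that clinically important abnormalities reach tables by another route. The Appendix 3 repeat applies to results judged clinically significant, and much the same judgement sends a result to the adverse event page (protocol 10.5.4) and to CTCAE grading (Appendix 2). In the example, ALT 9 × ULN is Grade 3 with a normal baseline. If treatment was interrupted for it, the event should count in the maximum-severity table and among TEAEs leading to interruption, whichever sample the window rule keeps. Targeted Medical Events are summarized too, though their list is not visible. All central values are listed, and in most timing combinations a scheduled peak is kept.

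This stands, and it rules out several stronger readings that a reader might infer:

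- *Laboratory safety is tabulated only as range-flag shifts.* Descriptive statistics with minimum and maximum are also planned.
- *A severe elevation can vanish from every table.* That does not follow for a result judged clinically significant.
- *The endpoint is not produced at all.* It is produced in part, through investigator judgement.
- *About 31% of peaks are lost.* The figure rests on assumed timings. The window table is not visible, and SAP 9.D, which summarizes at scheduled time points, leaves unclear whether a repeat competes with the scheduled draw. A locally run repeat is only listed and cannot displace a central value.
- *The plan breaks a promise to tabulate the liver criteria.* Protocol 10.5.7.1 is management guidance ("discontinuation of study treatment should be considered if any of the following occur"), and neither document undertakes to count subjects meeting it.

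The defence does not close the gap. Adverse event tables hold what investigators chose to record. In addition, the TEAE definition in SAP 9.C leaves out the protocol 11.8.2 limb covering events already present that worsen on treatment. As written, worsening of an abnormality present at treatment start could therefore miss the double-blind TEAE tables.

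**Conclusion.** The point holds as a reporting gap. The plan names incidence and severity of laboratory abnormalities as an endpoint, but its laboratory tables give neither a per-subject any-time count nor a grade. The one-value-per-window rule can leave a peak at a repeat or unscheduled draw, and sometimes a scheduled peak, to the listings alone. The remaining view, through adverse events, is partial and depends on investigator judgement.

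The size cannot be fixed from the documents. The incidence ranges and the 29% to 38% displacement shares illustrate the mechanism and do not estimate it. Some SAP safety subsections are redacted and the table shells are a separate document, so an output there cannot be excluded; the readable text of 9.D contains none. Efficacy conclusions are unaffected.

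**What to change.** - In SAP 9.D, add a shift from baseline to worst post-baseline CTCAE grade, with number and percentage of subjects, for each gradable parameter. Use all central laboratory values, including repeats and unscheduled draws, for the DB and OLE periods.
- In SAP 5.C, state that the closest-to-target rule applies only to by-visit summaries.
- Optionally, add a count of subjects meeting, at any time, the laboratory thresholds already listed in protocol 10.5.7.1.

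The cost is one or two extra tables and one sentence. The data are already collected and trial conduct does not change. If the tables are added after the primary lock and unblinding, SAP Section 1 requires them to be labelled ad hoc.

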This plan will cover the analyses for: 1) the primary database lock after the completion of the Double-Blind (DB) Treatment Period; 2) the final database lock after the completion of the Open-Label Extension (OLE) Period. The plan will be finalized before the time of primary database lock and treatment unblinding. After that, the SAP may be amended to accommodate ad hoc analyses before the final database lock. Ad hoc analyses will be labeled as such on the output and identified in the Clinical Study Report.

2. Protocol Objectives

A. Primary Objective

To assess the efficacy of etrasimod monotherapy (1 or 2 mg) in subjects with moderate to severe atopic dermatitis (AD) during the DB Treatment Period.

B. Safety Objective

To assess the safety and tolerability of etrasimod monotherapy (1 or 2 mg) in subjects with moderate to severe AD during the DB Treatment Period.

C. Open Label Extension Objective

To assess the long-term safety, tolerability, and efficacy of etrasimod monotherapy (2 mg) in subjects with moderate to severe AD.

3. Study Endpoints

A. Primary Efficacy Endpoint

Percent change in Eczema Area and Severity Index (EASI) from Baseline to Week 12.

[REDACTED]

B. Key Secondary Efficacy Endpoints

- Proportion of subjects achieving EASI-75, defined as a 75% reduction of EASI from Baseline to Week 12.
- Proportion of subjects achieving a validated Investigator’s Global Assessment (vIGA) of 0 or 1 (on a 5-point scale) and a reduction from Baseline of ≥ 2 points at Week 12.

C. Secondary Efficacy Endpoints

- Percent change in weekly peak pruritus numeric rating scale (NRS) from an itch daily diary from Baseline to Week 12.
- Proportion of subjects with improvement (reduction) in weekly peak pruritus NRS ≥ 3 from an itch daily diary from Baseline to Week 12.
- Proportion of subjects achieving EASI-50, defined as a $\geq 50\%$ reduction of EASI from Baseline to Week 12.
- Proportion of subjects achieving EASI-90, defined as a $\geq 90\%$ reduction of EASI from Baseline to Week 12.
- Change and percentage change in percent body surface area (BSA) AD involvement total and for each body region from Baseline to Week 12.

D. Exploratory Efficacy Endpoints

- Change in Dermatology Life Quality Index (DLQI) from Baseline to Week 12.
- Change in Patient Oriented Eczema Measure (POEM) from Baseline to Week 12.
- Percent change in SCORing Atopic Dermatitis (SCORAD), total and by symptom (severity, and subjective symptoms), from Baseline to Week 12.

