Data displays produced for this study will include three types - summary tables, data listings, and figures. Unless stated otherwise, data listings will be produced for all recorded data. Summary tables will be produced as specified in following sections. Additional data listings will be produced for outcome measures that involve extensive procedures to derive the analyzed outcomes. Figures will be produced when specified in sections to follow.

Data listings will simply list the data recorded on the eCRF or derived for each subject. In general, they will be ordered by treatment, subject number, and time of assessment. When expedient, additional levels of ordering hierarchy may reflect subsets of assessments within subject (e.g., further ordering by lab test names in the lab listings).

Summary tables will display summary statistics calculated for each of the treatment groups, unless described otherwise in following sections.

The Standard Display of table, listings, and figures (TLFs) and Precision of Data Displayed are documented in the appendix of SAP TLF Shell.

6. Subject Characteristics

Subject characteristics will be summarized overall and by treatment group for FAS, SAF, and PPS in the DB Treatment Period. Subject characteristics will be further summarized overall and by DB treatment group for OLE SAF in the OLE Period.

A. Demographics and Baseline Characteristics

- Age (years)
- Sex
- Race
- Ethnicity
- Region
- Weight (kg)
- Height (cm)
- Body mass index BMI (kg/m²)
- Baseline EASI score
- Baseline vIGA
- Baseline percent BSA AD involvement
- Baseline SCORAD total score
- Baseline peak pruritus NRS score from daily diary

B. Medical History/Atopic Dermatitis History

Medical history will be coded using Medical Dictionary for Regulatory Activities (MedDRA Version 23.0 March 2020) and summarized by system organ class (SOC) and preferred term (PT).

The following will be summarized for AD history:

- Time since AD diagnosis in years, calculated as the year of screening minus the year of first AD diagnosis
- Time since AD symptom in years, calculated as the year of screening minus year of first AD symptom
- Number of exacerbations in the last 12 months
- Hospitalization for complications of AD or side effects of treatment (Y, N)
- Prior use of AD therapy (Y, N), including phototherapy, biologics, Janus Kinase (JAK) inhibitors and other immunosuppressants
- Participation in prior dermatology clinical studies (Y, N)

7. Subject Accountability

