Clinically significant physical examination abnormalities will be included in medical history or recorded and summarized as an AE. The abnormal physical examination findings will be presented in a subject listing.

[REDACTED]

[REDACTED]

[REDACTED]

10. Other Assessments

[REDACTED]

[REDACTED]

[REDACTED]

[REDACTED]

11. Changes in Planned Analyses from the Protocol

A. Pairwise Correlation Coefficient among Efficacy Endpoints

Pairwise Pearson's correlation test will be performed for the following continuous efficacy endpoints for DB Treatment Period using FAS, observed cases. Pearson correlation coefficient and the corresponding p value will be presented.

- Percent change in EASI from Baseline to Week 12
- Percent change in diary based weekly peak NRS from Baseline to Week 12
- Change in %BSA total score from Baseline to Week 12
- Change in DLQI total score from Baseline to Week 12
- Change in POEM from Baseline to Week 12
- Change in SCORAD total score from Baseline to Week 12

Pairwise association test stratified by region and baseline vIGA will be performed for DB Treatment Period using FAS, observed cases using CMH test for the following binary endpoints:

- EASI -50/75/90 from Baseline to Week 12
- vIGA response from Baseline to Week 12
- Diary based weekly peak NRS ≥ 3 points reduction from Baseline to Week 12

B. COVID-19 Related Analysis Changes

In order to describe the impact of COVID-19 on current study, the following disposition events if any will be summarized:

- Subjects discontinued from the treatment/study as a result of a positive COVID-19 diagnosis under AE category.
- Subjects withdrawn due to COVID-19 pandemic. This is due to other reasons such as site closure, travel restrictions, fear of infection, etc. that are not related to COVID-19 diagnosis.

COVID-19 related protocol deviations will also be identified.

The above COVID-19 (including protocol deviation, treatment/study discontinuation and diagnosis of COVID-19) will be flagged at subject-level in corresponding data listings. Also, all COVID-19 related symptoms and confirmed cases occur during the study will be reported as AEs and included in the summaries. Subjects with study visits altered (including home visit, phone visits, etc) and missed due to COVID-19 will also be recorded in the database.

12. Post Hoc Analyses

A. Analyses with the Post Hoc Analysis Set

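### The endpoint-association tests in SAP 11.A make no allowance for treatment arm, and do not exclude the three EASI-threshold pairs that are associated by definition

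*SAP*

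**What the plan says.** SAP section 11.A, listed among the changes from the protocol, plans two sets of tests in FAS observed cases.

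- **Continuous endpoints.** A Pearson "correlation test will be performed for the following continuous efficacy endpoints for DB Treatment Period using FAS, observed cases". Six are listed: percent change in EASI and in weekly peak itch, and change in %BSA, DLQI, POEM and SCORAD. "Pearson correlation coefficient and the corresponding p value will be presented". No covariate, stratum or by-arm split is named.
- **Binary endpoints.** "Pairwise association test stratified by region and baseline vIGA will be performed for DB Treatment Period using FAS, observed cases using CMH test". The list is "EASI -50/75/90 from Baseline to Week 12", vIGA response, and a reduction of at least 3 points in weekly peak itch. That is five endpoints.

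Three other places bear on the reading.

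- SAP Table 2: "The FAS includes all randomized subjects, irrespective of whether they received any study treatment". All three arms are therefore in the set.
- SAP section 5.I, on displays: "Summary tables will display summary statistics calculated for each of the treatment groups, unless described otherwise in following sections".
- SAP Appendix 1, part C, specifies scatter plots with a correlation coefficient and there states that they are stratified by treatment. Section 11.A has no such words.

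**The concern.** Randomised treatment is a common cause of all these endpoints. If etrasimod lowers both EASI and itch, subjects on active drug tend to be low on both and subjects on placebo high on both. The two endpoints then correlate across the whole FAS even if, within each arm, a subject's EASI change says nothing about that subject's itch change. Stratifying by region and vIGA does not remove this, because randomisation balances those factors across arms.

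The second issue is independent of treatment. The three EASI thresholds cut the same Week 12 percent reduction, so a subject at EASI-90 is also at EASI-75 and EASI-50. A test of one against another only confirms the definition.

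What is at stake is how the association tables are read: correlations somewhat too large, p-values that do not test within-patient association, and three p-values with no content.

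**Working it through.** **Inputs from the plan** (SAP 4.C, Protocol 11.2): difference 35 percentage points for each active arm against placebo, SD 41, 1:1:1 allocation, 40 per arm, one-sided 0.025, drop-out up to 25%.

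**The plan's own figure.** A two-sample t-test with these inputs needs 30 evaluable subjects per arm (power 90.2%), and 30/0.75 = 40 per arm, 120 in all. The stated sample size reproduces. Observed-case analyses would then hold roughly 90 to 120 subjects. Section 11.A itself gives no figure.

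**Pooled Pearson correlation.** Let both endpoints shift by s SD in both active arms, with within-arm correlation r_w. The between-arm variance, in units of the within-arm variance, is b = s² × (1/3)(2/3), and

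pooled r = (r_w + b)/(1 + b).

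- s = 35/41 = 0.854, so b = 0.729 × 0.222 = 0.162.
- r_w = 0: pooled r = 0.162/1.162 = 0.139.
- r_w = 0.50: pooled r = 0.662/1.162 = 0.57.

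The critical |r| at two-sided 5% is 0.179 for n = 120 and 0.207 for n = 90. An r of exactly 0.139 gives p = 0.13 and 0.19.

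Simulated rejection rates with no within-arm correlation (normal errors, 6,000 runs per row):

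| Effect on both endpoints (SD) | Induced r | Pooled, 40/arm | Pooled, 30/arm | Arm-adjusted |
|---|---|---|---|---|
| 0 | 0 | 5% | 5% | about 5% |
| 0.25 | 0.01 | 5% | 5% | about 5% |
| 0.50 | 0.05 | 8% | 8% | about 5% |
| 0.854 (planning) | 0.14 | 33% | 27% | about 5% |
| 1.20 | 0.24 | 78% | 65% | about 5% |

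Repeat simulations at the planning effect gave 33–34% and 26–27%.

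**CMH, two responder endpoints independent within arm.** Assumptions: four equal strata (the region categories are redacted), placebo mean EASI improvement of 20, 30 or 40%, and active arms 35 points better.

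| EASI-75 rate, placebo / active | As planned, 40/arm | As planned, 30/arm | Arm added as stratum (40 / 30 per arm) |
|---|---|---|---|
| 9% / 31% | 11.7% | 8.8% | 4.8% / 5.2% |
| 14% / 40% | 13.7% | 11.9% | 5.0% / 5.2% |
| 20% / 50% | 15.6% | 13.0% | 4.4% / 5.2% |

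**Nested pairs.** Five binary endpoints give 5 × 4/2 = 10 pairs, and 3 of them lie within EASI-50/75/90. In the same simulations with no treatment effect at all, these pairs reached p < 0.05 in 94–100% of trials. With the 35-point effect they did so in all of them. As an illustration with assumed rates of 30% for EASI-75 and 12% for EASI-90, the definition alone gives

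phi = √[0.12 × 0.70/(0.30 × 0.88)] = √0.318 = 0.56.

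At n = 90 the chi-square is 90 × 0.318 = 28.6, p about 9 × 10⁻⁸. Adding arm as a stratum does not change this.

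**The case against.** **Pooling is not stated.** Section 11.A never says that the arms are combined, and the display rule in section 5.I could be read as implying results by arm. If the tests are run within arm, the treatment issue disappears. This stands in part. Against it, section 5.I governs the layout of summary statistics rather than the specification of tests, the CMH strata are listed and arm is not among them, and Appendix 1 names the treatment split where one is wanted. Pooling remains the natural reading, but two programmers could fairly produce different tables.

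**A reader might infer that the treatment effect alone makes these associations significant.** The figures do not support that. At the planning effect the expected induced r is below the critical value, about two-thirds to three-quarters of trials would show nothing, and CMH is affected less than Pearson. Only the nested pairs are near-certain to reach significance.

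**Zero within-arm correlation is an unrealistic null for many pairs.** SCORAD includes affected BSA and itch, and EASI grades extent. This also stands. For such pairs the relevant measure is the bias in r (0.50 becoming about 0.57), which is modest.

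**The SAP gives no purpose for 11.A.** An overall correlation across all randomised subjects is a legitimate description of how endpoints overlap. That is a reason to keep it beside an adjusted one, not a reason to omit the adjusted one.

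**The nested pairs are not named as pairs.** The three thresholds share one bullet, so pairing only across bullets is possible. The literal reading of a pairwise test includes them, and nothing excludes them.

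**Conclusion.** The point holds as a minor one. Read naturally, section 11.A mixes within-patient association with the shared treatment effect. With the planning effect of 0.85 SD on both endpoints and no within-arm correlation, Pearson rejects in about 26–34% of trials and CMH in about 9–16%, against a nominal 5%. A true r of 0.50 is shown as about 0.57. These figures assume the same standardised effect on both endpoints (the documents plan it only for EASI), normal errors, four equal strata and the response rates given above. At effects of 0.5 SD or less the Pearson rate is at most about 8%. The three nested EASI pairs are uninformative whatever the treatment effect.

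A reader might also infer that efficacy conclusions are compromised. The documents do not support that: this is an added, exploratory analysis, and no primary or key secondary result, sample-size choice or decision rule draws on it.

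**What to change.** In SAP section 11.A:

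1. State whether the tests are pooled or by arm.
2. If pooled, add treatment arm as a CMH stratum and report partial (arm-adjusted) or within-arm Pearson correlations. The unadjusted pooled values can stay beside them if an overall description is wanted.
3. Exclude the three pairs among EASI-50, EASI-75 and EASI-90 from testing; a cross-tabulation is enough. The other 10 − 3 = 7 binary pairs remain.

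The cost is one variable already in the data, fewer table rows and no new data collection. The drawback is sparser CMH strata. With four strata (assumed), adding three arms gives 12, an average of 120/12 = 10 subjects each, or 90/12 = 7.5 after 25% drop-out. In the simulations the test still held about 5% at that size. The partial correlation uses all subjects and gives up two degrees of freedom.
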